#### Table 1-2Treatment groups by subjects group for efficacy analysis

Evaluation of	Analysis Period	Treatment group label (order as listed)	Analysis
Subjects who were PASI 75 responders at Week 52	RW	AIN457 150 mg  AIN457 300 mg  AIN457 150 mg – Placebo  AIN457 300 mg – Placebo 	PASI 50/75/90/100 response and IGA 0 or 1 response Loss of PASI 75/IGA 0 or 1 response Time to relapse DLQI
Subjects who were re-treated after relapse with AIN457 150 mg or 300 mg	Treatment	AIN457 150 mg Placebo - AIN457 150 mg  AIN457 300 mg Placebo - AIN457 300 mg 	PASI 50/75/90/100 response and IGA 0 or 1 response
All subjects	On Treatment Period	AIN457 150 mg stay  AIN457 300 mg stay  All AIN457 150 mg  All AIN457 300 mg  AIN457 150 mg only  AIN457 150 mg - 300 mg  AIN457 300 mg only 	Final analysis

 AIN457 150mg group includes the PASI 75 responders at week 52 who were randomized to AIN150mg at week 52; and the partial responders at week 52 were continued received AIN 150mg from week 52.

 AIN457 300mg group includes the PASI 75 responders who were randomized to AIN300mg at week 52; and the partial responders at week 52 were continued received AIN 300mg from week 52.

Novartis	Confidential	Page 12
RAP Module 3	9-Apr-2018 (1:15)	Secukinumab / AIN457A2302E1

 AIN457 150mg – Placebo group includes the PASI 75 responders who were assigned AIN 457 150mg during core study, and randomized to placebo at week 52.

 AIN457 300mg – Placebo group includes the PASI 75 responders who were assigned AIN 457 300mg during core study, and randomized to placebo at week 52.

 Placebo – AIN457 150mg group includes the subjects who were randomized to placebo at week 52, and relapsed then treated by AIN457 150mg during RW period.

 Placebo – AIN457 300mg group includes the subjects who were randomized to placebo at week 52, and relapsed then treated by AIN457 300mg during RW period.

 AIN457 150 mg stay group includes the subjects who were PASI 75 responders at Week 52 and staying strictly in 150 mg AIN457 treatment from Week 52. The subjects received placebo at Week 52 and switched to AIN457 150 mg will not be included in this treatment group. Subjects up-titrated from AIN457 150 mg to 300 mg during open label period will not be included in this group.

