 AIN457 300 mg stay group includes the subjects who were PASI 75 responders at Week 52 staying strictly in 300mg AIN457 treatment from Week 52. The subjects received placebo at Week 52 and switched to AIN457 300 mg will not be included in this treatment group.

 All AIN457 150 mg group includes all the subjects who were assigned to AIN457 150 mg at Week 52, regardless whether they are initial PASI 75 responder or partial responder at Week 52, or who were assigned to placebo at week 52 but relapsed and retreated by AIN457 150 mg during randomized withdrawal period. The subjects who up titrated to 300 mg during the open label period will be included in the efficacy analysis for this treatment group. For the subjects assigned to placebo group at Week 52 and switched to AIN457 150 mg after relapse, the efficacy data after 16 weeks (including 16 weeks) post AIN457 treatment will be included in this group. In addition, the subgroup analysis will be performed for the following two subgroup groups: 1) Subjects who stayed on AIN457 150mg and never were up-titrated; 2) Subjects up-titrated from AIN457 150mg to 300mg during open label period.

All AIN457 300 mg group includes all the subjects who were assigned to AIN457 300 mg at Week 52, regardless whether they are initial PASI 75 responder or partial responder at Week 52, or who were assigned to placebo at week 52 but relapsed and retreated by AIN457 300 mg during randomized withdrawal period. For the subjects assigned to placebo group at Week 52 and switched to AIN457 300 mg after relapse, the efficacy data after 16 weeks post AIN457 treatment will be included in this group. The subjects up titrated during the open label period will not be included in this group.

AIN457 150 mg only group is from 'ALL AIN457 150 mg' group and includes the subjects who were PASI 75 responders or partial responder at Week 52 and staying strictly in 150mg AIN457 treatment from Week 52. The subjects received placebo at Week 52 and switched to AIN457 150 mg will not be included in this treatment group. Subjects up-titrated from AIN457 150mg to 300mg during open label period will not be included in this group.

 AIN457 150 mg - 300 mg group is from 'ALL AIN457 150 mg' group and includes the subjects who started AIN457 150 mg from Week 52 and up-titrated from AIN457 150mg to 300mg during open label period.

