For final analysis, the following treatment groups will be reported for the on treatment period.

AIN457 150 mg stay AIN457 300 mg stay All AIN457 150 mg All AIN457 300 mg AIN457 150 mg only AIN457 150 mg - 300 mg AIN457 300 mg only

The following study periods will be considered for analysis:

- Screening period (before Randomization in extension)
- **Randomized** withdrawal (RW) period for subjects who were PASI 75 responders at Week 52- the duration of RW period for each subject is different i.e., starting from Week 52 until the subject experiences the first full relapse for efficacy analyses and until the subjects reinitiating the secukinumab after first full relapse for safety analyses. RW period is not fixed for all the subjects but varies for subject to subject based on occurrence of relapse. Subjects not experiencing the relapse will end their RW period at Week 156.
- **Treatment** period for subjects with relapse (for efficacy analyses it is starting from the visit in RW period at which a subject experiences first full relapse to Week 156. Safety analysis will not be re-run for subjects with relapse).
- **Treatment** period for subjects with partial response (Week 52 to Week 156)
- **Open label** period for subjects who were continued in the study and were unblinded at Week 156. The first open label dose were given at the site at Week 156. Subjects previously randomized to receive 150 mg secukinumab may continue with 150 mg secukinumab open label or may switch to 300 mg s.c. at the discretion of the investigator. Subjects previously randomized to 300 mg secukinumab continued with 300 mg secukinumab open label. Placebo subjects who entered the open label period were given once weekly s.c. injections of secukinumab for 4 consecutive weeks and then s.c. injections every 4 weeks. Any subject starting on secukinumab 150 mg may continue on 150 mg every 4 weeks or switch to 300 mg at Week 156 or any other regular site visit if the investigator decided the subject would benefit from the higher dose. The Week 244 visit was the last scheduled visit at which the subjects were allowed to switch to 300 mg dose. Decreasing the dose from 300 mg to 150 mg was not allowed.
- Follow-up (FU) period (for all subjects)\*: treatment free period (Week 264 to Week 268).

Novartis	Confidential	Page 15
RAP Module 3	9-Apr-2018 (1:15)	Secukinumab / AIN457A2302E1

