## 1.9.6 Methods of analysis

## Final analysis

## PASI 50, PASI 75, PASI 90, PASI 100 and IGA 0 or 1 response over time

Descriptive statistics will be provided until the last visit. Summary statistics for PASI 50, PASI 75, PASI 90, PASI 100 and IGA 0 or 1 response by visit starting from Week 52 onwards will be presented in contingency tables and will include absolute and relative frequencies.

Confidence intervals for response rates will be derived as well based on the score method including continuity correction (Newcombe, 1998).

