# For subjects who were re-treated after relapse with secukinumab 150 mg or 300 mg

#### PASI 50, PASI 75, PASI 90, PASI 100 and IGA 0 or 1 response over time

Descriptive statistics will be provided from relapse until week 156. Summary statistics for PASI 50, PASI 75, PASI 90, PASI 100 and IGA 0 or 1 response by visit will be provided similar as for RW period.

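### The final four-year PASI/IGA tables select the 150 mg 'stay' and 'only' groups on a later dose switch, and replace the protocol's non-response rule with observed case, backed by an imputation model that stops at Week 68

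*SAP*

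**What the plan says.** **Groups.** SAP 1.3, Table 1-2, defines the columns of the final on-treatment tables.

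- '150 mg stay' (footnote 7) holds PASI 75 responders only: "Subjects up-titrated from AIN457 150 mg to 300 mg during open label period will not be included in this group".
- '150 mg only' (footnote 11) adds partial responders under the same rule: "Subjects up-titrated from AIN457 150mg to 300mg during open label period will not be included in this group".
- '150 mg - 300 mg' (footnote 12) "includes the subjects who started AIN457 150 mg from Week 52 and up-titrated from AIN457 150mg to 300mg".
- 'All 150 mg' (footnote 9) also takes in placebo subjects re-treated with 150 mg after relapse. It keeps switchers: "The subjects who up titrated to 300 mg during the open label period will be included in the efficacy analysis for this treatment group".

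**Timing.** Protocol 3.2 allows the switch from Week 156. SAP 1.3 gives the end: "The Week 244 visit was the last scheduled visit at which the subjects were allowed to switch to 300 mg dose". It also says: "Decreasing the dose from 300 mg to 150 mg was not allowed". Under SAP 1.9.6, PASI and IGA "response by visit starting from Week 52 onwards will be presented in contingency tables".

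**Missing data.** Protocol 9.4.3 counts a missing PASI or IGA response as non-response whatever the reason. It also plans to link follow-up data to missed visits, under schemes left to the analysis plan. SAP 1.9.4, under the final analysis, presents observed case, does not link follow-up data, and names multiple imputation as the sensitivity method for subjects on secukinumab from Week 52. SAP 1.9.4.2 fits that imputation by treatment group, lists changes from baseline through Week 68, and bars values after the primary endpoint time point. SAP 1.1.1 declares observed-data analysis only for rebound and relapse.

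**The concern.** A Week 68 response rate in 'stay' or 'only' depends on a decision taken 88 to 176 weeks later (156 - 68 and 244 - 68). No one assigned 300 mg is removed in this way, because the dose could not be reduced. '150 mg stay' is therefore read beside '300 mg stay' although only the first is selected on later switching. In the other direction, 'All 150 mg' shows data collected on 300 mg under a 150 mg label once a subject has switched.

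These are descriptive tables, but they carry the four-year maintenance result. Observed case hides how many subjects are no longer seen. The only planned analysis that could show how much this matters stops where the problem starts. Because SAP 1.1.1 is silent, a reader would not know that the protocol's rule has been replaced.

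**Working it through.** The documents give no switching rate and no open-label missing-data rate, so the plan has no figure of its own to reproduce here. Steps 1 to 3 use the documents alone. Steps 4 and 5 use assumed inputs.

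**1. Where a later switcher appears**

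| Column | Population | Later switchers before the switch | After the switch |
|---|---|---|---|
| 150 mg stay (fn 7) | PASI 75 responders | left out | left out |
| 150 mg only (fn 11) | PASI 75 and partial responders | left out | left out |
| 150 mg - 300 mg (fn 12) | switchers only | shown | shown, on 300 mg |
| All 150 mg (fn 9) | both, plus re-treated placebo subjects | shown | shown, on 300 mg |

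A subject switched at Week 244 has up to 244 - 52 = 192 weeks of 150 mg data outside 'stay' and 'only'.

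**2. Can an unselected rate be rebuilt?**

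For everyone assigned 150 mg at Week 52, yes: add the counts of 'only' and '150 mg - 300 mg'. For PASI 75 responders, no, because switchers are not shown separately for them. The two other planned tables do not fill the gap.

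- The randomized-withdrawal re-run stops at first relapse. Footnote 1 also puts partial responders into its 150 mg column, under a PASI 75-responder heading.
- For re-treated subjects SAP 1.9.6 says: "Descriptive statistics will be provided from relapse until week 156". SAP 1.5.4.1 counts those visits in days from relapse, so they cannot be added to the re-run by study week.

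**3. Reach of the imputation model (SAP Table 1-5)**

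- Weeks 56 to 156, every 4 weeks: (156 - 56)/4 + 1 = 26 visits.
- Weeks 168, 180, 192, 208, 220, 232, 244, 260: 8 visits. Total 34.
- In the written model: Weeks 56, 60, 64, 68, so 4 visits. Outside it: 30 of 34 (88%), including all 8 open-label visits.

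**4. Selection effect at Week 156 (assumed inputs)**

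Suppose 75% of the PASI 75 responders on 150 mg observed at Week 156 respond. Let *u* be the share of them who later switch and *r* the response rate of those switchers. Then

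stay = (0.75 - u × r) / (1 - u)

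| r | u = 0.1 | u = 0.2 | u = 0.3 | Shift, u = 0.1 to 0.3 |
|---|---|---|---|---|
| 0.60 | 76.7% | 78.8% | 81.4% | +1.7 to +6.4 points |
| 0.75 | 75.0% | 75.0% | 75.0% | 0 |
| 0.85 | 73.9% | 72.5% | 70.7% | -1.1 to -4.3 points |

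These inputs should not be carried back to early visits. At Week 68, with the 10% loss assumed in the sample size section, u = 0.3 and r = 0.60 would need (0.90 - 0.18)/0.7 = 103%, which is impossible. There r must be at least (0.90 - 0.70)/0.3 = 66.7%.

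**5. Observed case against non-response (assumed inputs)**

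Let the observed response be 80% and the missing share *m*. Non-response imputation gives 0.8(1 - m), the lower bound for all subjects. The upper bound is 0.8(1 - m) + m.

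- m = 0.2: 64% to 84%
- m = 0.4: 48% to 88%

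Observed case shows 80% in both. On the same subjects it can never fall below non-response imputation, since 0.8(1 - m) ≤ 0.8.

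**The case against.** The best defence is that no data are hidden. Switchers appear in 'All 150 mg' and in '150 mg - 300 mg', which meets the request in protocol Section 9 to summarize them as well. Footnotes 7 and 11 state openly that 'stay' and 'only' mean strictly on 150 mg. Footnote 9 adds a split of 'All 150 mg' by up-titration. This all stands, but none of it yields an unselected PASI 75-responder column over the on-treatment period. The footnote 9 split also conflicts with SAP 1.4, which plans no subgroup analyses for the final analysis.

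Footnote 10 also excludes up-titrated subjects, from 'All 300 mg'. However, it only keeps incoming switchers out and removes no one assigned 300 mg.

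The protocol's non-response rule has not vanished: SAP 1.9.4.1 keeps it for the randomized-withdrawal re-run, although SAP 1.9.4 names multiple imputation for the same variables. That re-run ends at relapse or Week 156.

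The imputation code is offered as an example, so a longer variable list would be easy to write. The bar on later values, though, is stated as a rule, and no other model is given.

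Linking of follow-up data is the weakest element, since protocol 9.4.3 leaves the scheme to the SAP. What remains is that the departure is not listed.

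On direction, subjects who dropped out before Week 156 contribute nothing at Week 156 under observed case. A downward shift there would have to come from other subjects who never switch, such as those seen at Week 156 who do not enter the open label period. At earlier visits, 'stay' does retain subjects who later drop out, whereas every switcher reached Week 156 and was judged to benefit at open-label entry.

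**Conclusion.** The concern holds and should be corrected. As written, two of the 150 mg columns are conditioned on a future event, and no on-treatment display follows all PASI 75 responders assigned 150 mg. Observed case replaces the protocol's rule without being listed, and the named sensitivity analysis cannot reach 30 of 34 visits.

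The primary test at Week 68 is not affected. The structural findings and the visit counts come from the documents. The percentage-point effects do not: they depend on assumed switching, response and missing-data rates. The selection effect is upward if switchers respond worse than stayers, zero if they respond alike, and downward if they respond better. The documents do not settle which applies.

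**What to change.** 1. Add a by-visit display of all PASI 75 responders assigned 150 mg at Week 52, with no exclusion for later up-titration. After Week 156, label it and 'All 150 mg' as 150 mg with optional increase to 300 mg. Label 'stay' and 'only' as selected on never switching.
2. At each visit give the numbers on 150 mg, switched, discontinued and observed.
3. Show the protocol's non-responder imputation beside observed case. Identify separately the subjects who ended at Week 156 by not entering the open label period.
4. Extend the multiple-imputation model to Week 260 using values after Week 68. State which groups it is fitted in, because the final groups overlap.
5. List observed case and the unlinked follow-up data in SAP 1.1.1, and reconcile footnote 9 with SAP 1.4.

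The cost is SAP wording and a few tables from data already collected. The drawback is that non-responder rates are lower bounds: they count as failures subjects who left at Week 156 as the protocol permits, which is why those subjects need their own line.

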#### Table 1-3 Treatment groups by subjects group for safety analysis

 Any AIN457 150 mg group includes all the subjects who have ever received at least one dose of AIN457 150 mg from Week 52 to Week 256 (Week 260 EOT no dose), regardless whether they are initial PASI 75 responder or partial responder at Week 52. For the subjects assigned to placebo group at Week 52 and switched to AIN457 150 mg after relapse or started AIN457 150 mg during open label period, the safety data during and after 1st AIN457 dose will be included in this group. For subjects starting with 150 mg AIN457 dose and switched to 300 mg AIN457, the period used the low dose will be counted for the 'Any AIN457 150mg' group.

 Any AIN457 300 mg group includes all the subjects who have ever received at least one dose of AIN457 300 mg from Week 52 to Week256 (Week 260 EOT no dose), regardless whether they are initial PASI 75 responder or partial responder at Week 52. For the subjects assigned to placebo group at Week 52 and switched to AIN457 300 mg after relapse or started AIN457 300 mg during open label period, the safety data during and after 1st AIN457 dose will be included in this group. For subjects starting with 150 mg AIN457 dose and switched to 300 mg AIN457 at any time, the period after switching to the high dose will be included in the 'Any AIN457 300 mg' group.

 AIN457 150mg – Placebo group includes the PASI 75 responders who were assigned AIN 457 150mg during core study, and randomized to placebo at week 52. Only data for subjects received placebo period were included in safety analysis.

 AIN457 300mg – Placebo group includes the PASI 75 responders who were assigned AIN 457 300mg during core study, and randomized to placebo at week 52. Only data for subjects received placebo period were included in safety analysis.

So, for re-run efficacy analysis the data will be analyzed for RW period. Regarding retreatment patients after relapse, the data till week 156 will be presented. For data analysis till week 156, the following treatment groups will be reported

#### • Subjects who were PASI 75 responders at Week 52

AIN457 150 mg AIN457 300 mg AIN457 150mg - Placebo AIN457300mg - Placebo

• Subjects who were re-treated after relapse with secukinumab 150 mg or 300 mg

AIN457 150 mg AIN457 300 mg Placebo - AIN457 150 mg Placebo - AIN457 300 mg

For final analysis, the following treatment groups will be reported for the on treatment period.

AIN457 150 mg stay AIN457 300 mg stay All AIN457 150 mg All AIN457 300 mg AIN457 150 mg only AIN457 150 mg - 300 mg AIN457 300 mg only

The following study periods will be considered for analysis:

- Screening period (before Randomization in extension)
- **Randomized** withdrawal (RW) period for subjects who were PASI 75 responders at Week 52- the duration of RW period for each subject is different i.e., starting from Week 52 until the subject experiences the first full relapse for efficacy analyses and until the subjects reinitiating the secukinumab after first full relapse for safety analyses. RW period is not fixed for all the subjects but varies for subject to subject based on occurrence of relapse. Subjects not experiencing the relapse will end their RW period at Week 156.
- **Treatment** period for subjects with relapse (for efficacy analyses it is starting from the visit in RW period at which a subject experiences first full relapse to Week 156. Safety analysis will not be re-run for subjects with relapse).
- **Treatment** period for subjects with partial response (Week 52 to Week 156)
- **Open label** period for subjects who were continued in the study and were unblinded at Week 156. The first open label dose were given at the site at Week 156. Subjects previously randomized to receive 150 mg secukinumab may continue with 150 mg secukinumab open label or may switch to 300 mg s.c. at the discretion of the investigator. Subjects previously randomized to 300 mg secukinumab continued with 300 mg secukinumab open label. Placebo subjects who entered the open label period were given once weekly s.c. injections of secukinumab for 4 consecutive weeks and then s.c. injections every 4 weeks. Any subject starting on secukinumab 150 mg may continue on 150 mg every 4 weeks or switch to 300 mg at Week 156 or any other regular site visit if the investigator decided the subject would benefit from the higher dose. The Week 244 visit was the last scheduled visit at which the subjects were allowed to switch to 300 mg dose. Decreasing the dose from 300 mg to 150 mg was not allowed.
- Follow-up (FU) period (for all subjects)\*: treatment free period (Week 264 to Week 268).

Novartis	Confidential	Page 15
RAP Module 3	9-Apr-2018 (1:15)	Secukinumab / AIN457A2302E1

- Follow-up 2 (FU 2) period: treatment free period only for subjects who prematurely discontinued treatment. All subjects who prematurely discontinued treatment should complete all assessment of Week 260 (end of treatment visit) and of the follow-up period visits (Weeks 264 and 268). Subsequently, adverse events and use of concomitant medication were evaluated by the investigator through telephone calls every 3 months for duration of 4 years from the time when subject has been enrolled into CAIN457A2302E1 study.
- Entire study period = Combination of RW period + treatment period for subjects with relapse and treatment period for subjects with partial response + open label period (Week 156 Week 260) + follow-up period (Week 264 Week 268).
- On treatment period = Combination of RW period + treatment period for subjects with relapse and treatment period for subjects with partial response + open label period (Week 156 Week 260).

The number of subjects in the analysis sets may differ between the study periods listed above.

The primary and secondary efficacy variables for final analysis are described as in table 1-4.

Endpoint/analysis	is Period					
	RW	treatment (re-treated after relapse)	treatment (partial responders)	On treatment period	Follow-up	Entire study period
Demography & baseline characteristics	Х					Х
Previous & concomitant medication						Х
Medical history						Х
Study medication: duration of exposure						Х
Loss of PASI 75 response over time after 52 weeks of treatment	Х					
PASI 50/75/90/100 and IGA mod 2011 0 or 1 response over time	Х	X 		Х		
Loss of IGA 0 or 1 response over time after 52 weeks of treatment	X 					

Table 1-4Analysis by period

Endpoint/analysis		Period				
	RW	treatment (re-treated after relapse)	treatment (partial responders)	On treatment period	Follow-up	Entire study period
PASI score over time				Х		
IGA mod 2011 score over time				Х		
Relapse					Х	
Rebound					Х	
EQ-5D				Х		
DLQI	Х			Х		
HAQ © -DI				X 		
DLQI 0 or 1 achievement	Х			Х		

X: for subjects who re-treated with secukinumab

X for subjects with PSA at baseline of the core study

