### 2.2 Secondary objectives

- To assess the efficacy of secukinumab 150 mg or 300 mg with respect to PASI 50/75/90/100 response and IGA 0 or 1 response, compared to placebo over time in subjects who were PASI 75 responders at Week 52, over time for subjects who were re-treated after relapse with secukinumab 150 mg or 300 mg, and over time in subjects who were partial responders at Week 52
- To assess the efficacy of secukinumab 150 mg or 300 mg with respect to PASI score and IGA mod 2011 score, compared to placebo over time in subjects who were PASI 75 responders at Week 52, over time for subjects who were re-treated after relapse with secukinumab 150 mg or 300 mg, and over time in subjects who were partial responders at Week 52
- To assess time to PASI 75 response **for subjects who were re-treated after relapse with secukinumab 150 mg or 300 mg.**
- To assess the efficacy of secukinumab 150 mg or 300 mg in subjects with moderate to severe chronic plaque-type psoriasis with respect to loss of IGA 0 or 1 response, compared

to placebo **in subjects who were PASI 75 responders and IGA 0 or 1 responders at Week 52.**

- To assess time to IGA 0 or 1 response for subjects who were IGA 0 or 1 responders at re-randomization, and who lost IGA 0 or 1 response during randomized withdrawal, and **who were re-treated after relapse with secukinumab 150 mg or 300 mg.**
- To assess the clinical safety of secukinumab 150 mg or 300 mg as assessed by vital signs, clinical laboratory values, electrocardiograms (ECGs), and adverse events (AEs) monitoring, compared to placebo in subjects who were PASI 75 responders at Week 52, in subjects who were re-treated after relapse with secukinumab 150 mg or 300 mg, and in subjects who were partial responders at Week 52.
- To assess the efficacy of secukinumab 150 mg or 300 mg in subjects with moderate to severe chronic plaque-type psoriasis with respect to changes in Dermatology Life Quality Index® (DLQI®), compared to placebo over time in subjects who were PASI 75 responders at Week 52, over time for subjects who were re-treated after relapse with secukinumab 150 mg or 300 mg, and over time in subjects who were partial responders at Week 52.

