## **9.5.2 Safety variables**

All safety evaluations will be performed on the Safety set. For adverse events an analysis based on pooled treatment groups “any secukinumab 150 mg” and “any secukinumab 300 mg” will also be done. In the analysis of the subjects who were re-treated after relapse with secukinumab 150 mg or 300 mg only safety data after re-treatment after relapse will be reported. With the exception of adverse events that qualify as "treatment emergent" (see definition below), data collected from telephone visits and unscheduled visits in follow-up period 2 will only be included in individual patient listings, but not in summary tables.

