# 1.10 Standard safety evaluation

All safety analyses will be based on the safety set. In general, summaries will be provided for extension phase i.e after first dose of study medication in extension. In general, extension baseline will be used for all change from baseline analysis.

Safety analysis will be based on treatment groups as defined in Table 1-3.

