## 1.10.1 Adverse events

Adverse events will be summarized for entire study period.

For adverse events and other binary safety variables crude incidence and exposure timeadjusted incidence will be derived as described below and summarized in Table 1-15.

All adverse events are summarized based on treatment emergent only. The definition for "treatment emergent" is as below:

- 1. events started after the first dose of study medication or events present prior to the first dose of study medication but increased in severity based on preferred term
- 2. and started prior to the last dose plus 84 days (inclusive)

All adverse events will be listed with "treatment emergent" flag displayed.

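### In the final analysis no AE, vital-sign or ECG summary compares the four randomised groups over the withdrawal period, and for Weeks 68 to 156 the documents commit to no randomised safety comparison with placebo

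*SAP*

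**What the plan says.** **Protocol.** Section 2.2 sets a safety objective covering vital signs, laboratory values, ECGs and "adverse events (AEs) monitoring, compared to placebo in subjects who were PASI 75 responders at Week 52, in subjects who were re-treated" subjects and partial responders, so the three populations are named separately. Section 9 lists four analysis groups for the PASI 75 responders: each dose and its own placebo. Re-treated subjects and partial responders are separate groups. Section 9.5.2 then adds the pooling: "For adverse events an analysis based on pooled treatment groups “any secukinumab 150 mg” and “any secukinumab 300 mg” will also be done".

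**SAP.** Section 1.10 states: "Safety analysis will be based on treatment groups as defined in Table 1-3". For the entire study period that table has five columns: Any 150 mg, Any 300 mg, Any dose, and two placebo groups. Its first footnote says: "Any AIN457 150 mg group includes all the subjects who have ever received at least one dose of AIN457 150 mg from Week 52"; the second says the same for 300 mg. Both admit responders and partial responders alike, including placebo subjects after relapse or from open-label start. Any 300 mg also takes the time after up-titration from 150 mg. The placebo columns keep placebo time only.

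On the period, SAP 1.10.1 says: "Adverse events will be summarized for entire study period". Sections 1.10.2 to 1.10.4 say the same for laboratory data, vital signs and ECG. The study-period list in SAP 1.3 gives the RW period its own safety end point, "until the subjects reinitiating the secukinumab after first full relapse for safety analyses", but SAP 1.1 and 1.3 re-run only efficacy for that period.

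**The concern.** The RW period is the only part of the study with a concurrent, blinded, randomised placebo control. A reader of the final report who wants the safety comparison in the objective will find placebo printed beside Any AIN457 and will compare the two. Those columns differ in four ways:

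- **Population:** partial responders appear only on the secukinumab side.
- **Time:** secukinumab time can run to the end of the study, placebo time only to relapse or Week 156.
- **Blinding:** open-label years are on one side only.
- **Membership:** re-treated placebo subjects contribute to both sides.

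A difference, or its absence, could not be put down to continuing versus stopping secukinumab. Protocol 9.5.2 made pooling an extra, and for adverse events only. The SAP makes it the sole basis for all safety domains, and SAP 1.1.1 does not list this as a change.

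**Working it through.** **1. Which final-analysis safety output covers the randomised groups over the RW period?**

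- *AEs, vital signs, ECG:* Table 1-3 groups, entire study period. No column holds the randomised continuing arms.
- *Laboratory shift tables:* SAP 1.1.1 takes the most extreme value within the RW or the treatment period, while SAP 1.10.2 uses the entire study period. If 1.1.1 governs, an RW-period shift table would in effect be randomised, since only PASI 75 responders have an RW period. If 1.10.2 governs, it would not. The two must be reconciled.
- *AEs by year interval (SAP 1.10.1):* these can separate the blinded from the open-label years, but still within the pooled groups.
- *Exposure-adjusted rates:* the overview table in SAP 1.10.1 plans them for AEs, special-interest risks, SAEs and SMQs, and SAP 1.10.2 adds CTCAE laboratory grades. That overview lists severity, treatment-related AEs, deaths and notable values as crude incidence only.

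**2. What is covered elsewhere?** Protocol 9.6 plans analysis of all data to Week 68, with the sponsor unblinded. That is 68 − 52 = 16 of the 156 − 52 = 104 RW weeks. Protocol 3.3 predicts full relapse reaching only 10% four months after withdrawal, so on the protocol's own prediction most placebo subjects would still be in blinded RW after Week 68. Beyond that, Protocol 9.6 says only that further interim analyses may be done.

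**3. Make-up of an Any-dose group (illustration).** Inputs: 414 RW subjects per dose at 2:1 (Protocol 9.7) and about 1,220 in total (Protocol 4).

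- 414 × 2/3 = 276 active and 138 placebo, which reproduces the plan's figures.
- 1,220 − 2 × 414 = 392 partial responders; assumed equal by dose, 196 each.
- No placebo subject later treated: 276 + 196 = 472; 276/472 = 58%.
- Half later treated: 276 + 196 + 69 = 541; 276/541 = 51%.
- All later treated: 276 + 196 + 138 = 610; 276/610 = 45%.

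Up-titrated subjects would lower the share in Any 300 mg further.

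**4. Share of Any 150 mg person-time that is the randomised arm's two blinded years (illustration, no drop-out).** The numerator is 276 × 2 = 552.

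- No placebo subject treated, no up-titration: 552/[(276 + 196) × 4] = 552/1,888 = 29%.
- No relapse, all placebo subjects start 150 mg open label for 2 years: 552/(1,888 + 138 × 2) = 552/2,164 = 26%.
- All placebo subjects re-treated for 3.5 years: 552/(1,888 + 138 × 3.5) = 552/2,371 = 23%.
- As the last case, but everyone up-titrates at Week 156: 552/(276 × 2 + 196 × 2 + 138 × 1.5) = 552/(552 + 392 + 207) = 552/1,151 = 48%.

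**5. Effect of unequal time on crude incidence.** Assume the same constant rate of 0.05 per year on drug and placebo; incidence = 1 − exp(−rate × years).

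- Placebo for 0.5, 1 or 2 years: 2.5%, 4.9%, 9.5%.
- Secukinumab for 4 years: 18.1%.
- Ratios: 7.3, 3.7, 1.9, with no drug effect.

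Over rates from 0.01 to 0.20 per year the ratio ranges from 7.9 to 1.7. Exposure adjustment removes this part of the imbalance where it is planned. It does not remove the population mix.

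**The case against.** The SAP says it mainly covers the final analysis and that key analyses were done before. It also says that data are analysed according to Protocol 9, which supplies the four randomised groups, and the Week 68 analysis takes in all data to that point. A reader might infer from Table 1-3 that the randomised safety comparison is never made. The documents do not support that, because a comparison to Week 68 is implied. What stands is the gap from Week 68 to Week 156.

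A reader might also infer that the RW period plays no part in SAP safety text. That too goes further than the text: SAP 1.1.1 mentions it for laboratory shift tables, and SAP 1.5.6 takes exposure to the last RW visit.

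Nor do the documents show that placebo data come mostly from the first months after withdrawal. Placebo can run to Week 156, and the relapse prediction in Protocol 3.3 points the other way.

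The pooled groups are pre-specified for AEs, and the SAP tables are descriptive, with no safety test against placebo and no claim to be a randomised comparison. That is fair and limits the harm. It does not supply the comparison that the objective names, and the tables carry no caveat.

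Finally, RW tables have a weakness of their own. RW time ends at relapse or re-initiation, so its length depends on outcome and differs by arm. This stands, and it shapes the fix.

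**Conclusion.** The point holds for the final analysis. On SAP 1.10 and Table 1-3, no AE, vital-sign or ECG summary sets the four randomised groups side by side over the RW period, and the laboratory shift tables are contradictory on this. For Weeks 68 to 156 the documents commit to no randomised safety comparison, although Protocol 2.2, 9 and 9.5.2 call for one, and SAP 1.1.1 is silent. Year-interval and exposure-adjusted summaries reduce the time imbalance but leave the population mix.

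The size is illustrative. The randomised arm is about 45% to 58% of each Any-dose group, assuming the planning numbers, partial responders split equally by dose, and no up-titrated subjects counted. Amendment 2 reports 1,146 randomised rather than 1,220, and the 414 applies the 150 mg response rate to both doses. A reader might take the 23% person-time share as an upper bound, but it is not one: the Any 150 mg cases above run from 23% to 48%, depending on relapse and up-titration. The conclusion rests on the group and period definitions, not on these percentages.

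**What to change.** In SAP 1.3 and 1.10, add RW-period safety tables for the four randomised PASI 75 responder groups, each dose against its own placebo, using the RW safety definition already in SAP 1.3. Cover AEs, SAEs, AEs leading to discontinuation, deaths, notable laboratory values, vital signs and ECG. Make exposure-adjusted rates the main measure and show crude rates alongside, because RW time differs by arm.

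Footnote the Any AIN457 tables as not a randomised comparison. Declare the change from Protocol 9.5.2 in SAP 1.1.1, and reconcile 1.1.1 with 1.10.2 on the period for laboratory shift tables. If an earlier report already holds this comparison to Week 156, cite it.

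The cost is SAP wording and one more table set from data already collected. The randomised tables will have fewer person-years and wider intervals, and their outcome-dependent follow-up must be stated with the results.
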